1.2. Secondary Objectives

To define the PSA response rate (50% reduction, with 30% reduction exploratory analysis).

To define the duration of PSA response

To define the toxicity of ¹⁷⁷Lu-J591 given as single dose plus ketoconazole in men with castrate resistant biochemical disease.

To assess the overall and prostate cancer specific survival rate of patients following treatment.

To define the toxicity and need for dose modifications with “high dose” ketoconazole in men with biochemically progressive castrate resistant prostate cancer

To assess the prognostic implications of baseline adrenal hormone levels in men with castrate resistant non-metastatic prostate cancer receiving ketoconazole

To explore the ability of ¹⁷⁷Lu-J591 to image metastatic sites in patients who are NED on bone scan CT/MRI of abdomen/pelvis and CXR (selected study sites)

To assess the changes with therapy and implications of plasma markers of hemostasis, fibrinolysis, and angiogenesis in biochemically progressive castrate resistant prostate cancer (optional)

To assess patient reported outcomes with high-risk, non-metastatic CRPC and with the development of metastases

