9.2 Special Studies

9.2.1 Radiolabeled-J591 Imaging

9.2.1.1 Assessment

9.2.1.1.1 Method of Assessment:

Planar imaging will be performed 2-8 days after radiolabeled-J591 administration (scan window will be assigned at randomization). In the case of a suspicious lesion, SPECT of the area may be performed at the nuclear med physician's discretion. In addition a CT/MRI may be obtained for possible confirmation. Identified sites will be followed on subsequent imaging modalities (bone scan, CT or MRI) to define the interval between identification of the lesion/s by radiolabeled-J591 versus other modalities. Images will be captured as specified in the Imaging Manual and provided to WCMC on disc in dicom format.

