13.4 Analysis of Secondary & Exploratory Endpoints

Secondary endpoints include biochemical (PSA) response rate, duration of PSA response, biochemical (PSA) progression, time to biochemical (PSA) progression, time to biochemical (PSA) progression above baseline, overall survival, and toxicity. We anticipate that the 95% confidence interval around the PSA response rate will be within $\pm 9\%$ of the true value for Arm 1 and within $\pm 15\%$ of the true value for Arm 2. Time to biochemical (PSA) progression, time to biochemical (PSA) progression above baseline, median MFS-time, and overall survival will be estimated using the Kaplan-Meier method, and 95% confidence intervals will be calculated using Greenwood's formula.

The frequency of subjects experiencing toxicities will be tabulated. Toxicities will be assessed and graded according to CTCAE v. 4.0 terminology. Exact 95% confidence intervals around the toxicity proportions will be calculated to assess the precision of the obtained estimates.

Imaging studies: The possibility of identifying sites of metastatic disease not apparent on conventional imaging (CT/MRI abdomen/pelvis, bone scan, and CXR) will be confirmed with serial imaging. Any potential metastatic site on J591 imaging will be followed over time by conventional imaging. Sites of disease appearing on J591 scan and subsequently confirmed by conventional imaging will be labeled as positive. Any site apparent on J591 scan that is subsequently biopsied as part of standard care and confirmed to be metastatic prostate cancer will be labeled as definite. Sites of disease appearing on J591 scan without any corroborating evidence (conventional imaging or biopsy) will be labeled as possible.

Adrenal hormonal levels: Baseline adrenal hormonal levels will be categorized by median baseline levels found in CALGB 9583 (60, 61). In addition, as this may be a different patient population, we will analyze by median as well as quartiles. We will correlate levels with time to radiographic metastatic disease as well as PSA response and overall survival. Changes in adrenal hormone levels will be analyzed with time (baseline, 1 month, 6 months, at progression).

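### The J591 imaging rule in 13.4 scores only sites that J591 shows, so it cannot count missed lesions, separate out refuted foci, or gauge how much agreement is chance

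*Combined protocol and SAP*

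**What the plan says.** Section 1.2 lists the aim among the secondary objectives, in exploratory wording: "To explore the ability of ¹⁷⁷Lu-J591 to image metastatic sites in patients who are NED on bone scan" and the other conventional scans, at selected study sites. The synopsis extends it to 111In-J591.

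The Imaging studies paragraph of 13.4 says that the possibility of finding metastases not apparent on conventional imaging "will be confirmed with serial imaging", and then: "Any potential metastatic site on J591 imaging will be followed over time by conventional imaging". Three labels follow:

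- *Positive*: "Sites of disease appearing on J591 scan and subsequently confirmed by conventional imaging will be labeled as positive".
- *Definite*: "Any site apparent on J591 scan that is subsequently biopsied as part of standard care and confirmed to be metastatic prostate cancer will be labeled" with that word.
- *Possible*: "Sites of disease appearing on J591 scan without any corroborating evidence (conventional imaging or biopsy) will be labeled as possible".

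Section 9.2.1.1.1 has the same starting point: "Identified sites will be followed on subsequent imaging modalities (bone scan, CT or MRI) to define the interval" between detection by J591 and by the other modalities. It also allows SPECT, and an extra CT or MRI, where J591 shows a suspicious lesion.

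Neither section gives a denominator, a time limit for confirmation, a comparison with J591-negative sites or men, or a number of confirmed sites that would settle the question.

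**The concern.** The ability to image metastases has two sides: how often a focus proves real, and how often a real metastasis was shown. The rule takes in only J591-visible sites, so the second side is never recorded. On the first side, a focus that has been refuted shares a label with one that has simply not yet been followed for long.

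Many of these men are expected to develop metastases, so some later lesions may fall on J591 foci by coincidence. Suspicious J591 sites may also be examined more closely than other sites. The planned interval between modalities is measured only for lesions that J591 identified, so lesions it missed are left out of that too.

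At stake is whether the imaging objective, which has its own scan visit and is one stated reason for using 111In-J591 as placebo (13.1.1), gives an answer that a reader can interpret.

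**Working it through.** **Step 1. What each possible finding becomes under 13.4**

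| Finding | Label |
|---|---|
| J591 focus, later seen on conventional imaging | *positive* |
| J591 focus, biopsy shows metastatic prostate cancer | *definite* |
| J591 focus, not yet followed for long | *possible* |
| J591 focus, negative on all later scans or on biopsy | only *possible* is left |
| Conventional metastasis, no J591 uptake there | none |
| J591-negative man, with or without later metastasis | none |

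The gap is in the last three rows. It needs no assumption.

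**Step 2. Expected events**

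The imaging paragraph states no figure, so the event count comes from the primary design in 13.1: 34 and 17 men, 18-month metastasis-free survival (MFS) of 80% and 50%, one-sided alpha 10%. That design reproduces:

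- pooled proportion (34 × 0.80 + 17 × 0.50)/51 = 0.70
- null SE = √[0.70 × 0.30 × (1/34 + 1/17)] = 0.136
- alternative SE = √[0.16/34 + 0.25/17] = 0.139
- power = Φ[(0.30 − 1.282 × 0.136)/0.139] = 81.6%, against the stated minimum of 80%

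Expected MFS events by 18 months are 34 × 0.20 + 17 × 0.50 = 15.3 of 51 (30%). If both arms had 50% MFS, they would be 25.5. For scanned men with metastases these are upper limits, because 13.1 also counts deaths and only selected sites scan.

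**Step 3. Chance of at least one coincidental *positive* site from an uninformative scan**

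Let M be the scanned men who later develop metastases, f the share of men with a flagged site unrelated to disease, and q the chance that the flagged site coincides with a later metastatic site. Assume one flag per man and independent men. The documents give neither f nor q; both are assumed.

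P = 1 − (1 − f·q)^M

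| f, q | M = 8 | M = 16 | M = 27 |
|---|---|---|---|
| 0.1, 0.1 | 8% | 15% | 24% |
| 0.2, 0.1 | 15% | 28% | 42% |
| 0.2, 0.2 | 28% | 48% | 67% |
| 0.3, 0.2 | 39% | 63% | 81% |
| 0.3, 0.3 | 53% | 78% | 92% |
| 0.5, 0.3 | 73% | 93% | 99% |

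P passes one half only if f·q exceeds 1 − 0.5^(1/M): 0.083 for M = 8, 0.042 for M = 16, 0.025 for M = 27.

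**Step 4. A second model as a cross-check**

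Place 1 to 3 foci and 1 to 3 metastatic regions at random among 10 body regions (assumed). The overlap probability runs from 1/10 = 0.10 to 1 − C(7,3)/C(10,3) = 1 − 35/120 = 0.71. Multiplied by the 30% event rate, this is 0.03 to 0.21 per scan-positive man. For N scan-positive men, P = 1 − (1 − 0.30c)^N, where c is the overlap probability:

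- N = 20: 0.46 to 0.99
- N = 10: 0.26 to 0.91
- N = 5: 0.14 to 0.70

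Both models agree that coincidental *positive* sites are a real prospect and that their frequency cannot be pinned down.

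**The case against.** A reader might infer that a useless scan would usually be declared confirmed. The documents do not support that. Section 13.4 sets no criterion for confirmation; taking one *positive* site as enough is an assumption added here. Even on that assumption, the lower ends of both models are below one half, and the number of men scanned is unknown.

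A reader might also infer that no result could count against the scan. That is too strong. The labels cover all J591 foci, so the fraction *positive* or *definite* could be computed, although the plan does not name it. In the low case of step 4 with 20 men and one focus each, the expected yield is 20 × 0.03 = 0.6 matches. A report of one *positive* and 19 *possible* sites would be unfavourable. Nor is *possible* simply an affirmative label: the text defines it by the absence of corroboration. The interval in 9.2.1.1.1 would also reveal late matches as late.

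The obvious full remedy, scoring every body region to 18 months, does not fit the schedule. Study calendar note 11 puts end of study at first documented metastasis, and no serial scans are scheduled after that, so the remaining regions would be unobserved rather than negative. A comparison of J591-positive with J591-negative sites pooled over arms would be confounded, because 177Lu is meant to treat the sites that take it up.

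Finally, the objective is exploratory in wording, and imaging is not in the list of secondary endpoints that opens 13.4. That limits the weight of the point. What none of this answers is that missed metastases are never counted and refuted foci are not separated from those still awaiting follow-up.

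**Conclusion.** The concern holds in a limited, structural form. The rule in 13.4, with 9.2.1.1.1, labels and follows only J591-visible sites. It has no category for a conventional metastasis that J591 did not show, none for a refuted focus, no follow-up window and no denominator. This follows from the text alone. Applied as written, it gives a one-sided answer to the imaging objective.

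The size of the chance-agreement problem is not established. The ranges in steps 3 and 4 rest on assumed flag rates, overlap, region map and numbers scanned. They show only that an uninformative scan could yield *positive* sites that the plan could not distinguish from detection. The primary analysis is unaffected. The change is worth making because it is cheap.

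**What to change.** Amend the Imaging studies paragraph of 13.4 as follows.

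- **Population and window.** Include every man with a J591 scan, scan-negative men among them. Follow each to first conventional metastasis or 18 months, whichever is earlier.
- **Labels.** Add *not seen on J591* for a site of first conventional metastasis with no J591 uptake. Add *not confirmed* for a J591 focus still negative at the end of that window, or negative on biopsy.
- **Estimates, with 95% confidence intervals.** Report the proportion of J591 foci confirmed, the proportion of first conventional metastatic sites that J591 had shown, and metastasis rates in J591-positive versus J591-negative men. Intervals for foci should allow for several foci in one man.
- **By arm.** Present all of this separately by arm. Read *not confirmed* as a likely false positive only in the 111In arm, since 177Lu may have treated the focus.

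The cost is one paragraph and a little more analysis. J591 scans are already assessed centrally (9.2.1.1.2), and conventional scans are already scheduled every 6 months, then every 3 months after PSA progression. Numbers will be small: at most about 17 men in the 111In arm, with about 17 × 0.50 = 8.5 MFS events, and fewer if only some sites scan. Metastases that arise after the J591 scan will count as not seen, so the figures will look less favourable than a count of confirmed sites. They describe prediction over the window rather than detection on the day of the scan, and the report should say so.

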5.1.3 Radiolabeled J591

Eligible patients will receive a single dose of ^{177}Lu -J591 (70 mCi/m²) or ^{111}In -J591 (5 mCi) on a Thursday or Friday approximately 4 weeks after cycle 1, day 1 consisting of J591 chelated at a specific activity of 12-15 mCi of ^{177}Lu per mg of antibody plus sufficient non-radiolabeled, non-DOTA-conjugated ("naked") J591 to achieve a total antibody dose of 20 mg. Each dose will be administered by an IV infusion at a rate not to exceed 5 mg/min.

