9.2.1.1.2 Timing of Assessment

J591 scanning will be performed approximately 2-3 or 6-8 days after J591 administration (scan date will be assigned with randomization). Scans will be assessed centrally at WCMC.

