- Electrolytes, BUN, Creatinine*
- PSA*
- Total protein, albumin, calcium, total bilirubin, AST, ALT, LDH
- Alkaline phosphatase
- Plasma markers
- Adrenal hormones
- CTC's
- Concomitant medications
- Concomitant/interval procedures
- Adverse events (pre- and post- infusion)

*Note that treatment day labs are used for radiolabeled-J591 baseline (not for assessment of eligibility)

Evaluations and procedures at Visit 4/J591 Scan (C2D3-9)

- Adverse Events
- Concomitant medications
- Concomitant/interval procedures
- J591 imaging (2-8 days after infusion). At selected study sites, whole body planar radionuclide images will be obtained between 2-8 days post-J591 treatment. The date of scan (3 or 4 days vs 6-8 days after J591 infusion) will be assigned at the time of randomization. SPECT studies of sites of disease will be obtained in selected patients as appropriate. These will be used to assess the ability of radiolabeled J591 to image

metastatic sites that do not appear on conventional imaging modalities (bone scan, CT/MRI).

Evaluations and procedures C2D22 (safety CBC for some subjects)

For subjects on aspirin/NSAIDs with anti-platelet properties or anticoagulation, a CBC on approximately Day 50 is **required** (3 weeks +/- 2 days after radiolabeled J591 infusion). For all other subjects, in particular subjects with baseline platelet counts < 200/mm³ a CBC at this timepoint is suggested, but not required.

- CBC with differential †

Evaluations and procedures C3D1

- Interval medical history
- Targeted Physical Examination
- Vital Signs
- ECOG Performance Status
- Verification of ketoconazole/hydrocortisone administration, Collection/Distribution of diary
- Adverse Events
- Concomitant medications
- Concomitant/interval procedures
- CBC with differential and platelet count.
- Electrolytes, BUN, Creatinine
- Total protein, albumin, calcium
- Total bilirubin, AST, ALT, alkaline phosphatase, LDH
- PSA
- Plasma markers
- CTCs

Evaluations and procedures Cycle 3 D8 *†

- CBC with differential and platelet count

Evaluations and procedures Cycle 3 D15 *†

- CBC with differential and platelet count†

Evaluations and procedures Cycle 3 D22 *†

- CBC with differential and platelet count†

All CBC results during cycle 3 must be either entered into the REDCap eCRF database or emailed to [contact] within 24 hours of testing.

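### The imaging labels in Section 13.4 cover only J591-positive sites, so yield and lead time can be estimated but detection rate, negative predictive value and false-positive rate cannot

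*Combined protocol and SAP*

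**What the plan says.** Section 1.2 lists as a secondary objective an exploration of the ability of 177Lu-J591 "to image metastatic sites in patients who are NED on bone scan CT/MRI of abdomen/pelvis and CXR", at selected study sites. The protocol summary names 111In-J591 as well.

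Section 13.4 sets out how the scans are to be judged. On follow-up: "Any potential metastatic site on J591 imaging will be followed over time by conventional imaging." On confirmed sites: "Sites of disease appearing on J591 scan and subsequently confirmed by conventional imaging will be labeled as positive." A J591 site that is biopsied in routine care and proves to be metastatic prostate cancer is *definite*. For the rest: "Sites of disease appearing on J591 scan without any corroborating evidence (conventional imaging or biopsy) will be labeled as possible."

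Section 9.2.1.1.1 adds that identified sites are followed to measure the interval between detection by J591 and by other modalities. Section 9.2.1.1.2 has the J591 scans read centrally. Conventional imaging is repeated in all men every 6 months, and every 3 months after PSA progression (Section 10 footnotes and Section 10.1). No section states whether the unit of analysis is the site or the man, or when *possible* becomes final.

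On scan timing, Section 9.2.1.1.2 says "J591 scanning will be performed approximately 2-3 or 6-8 days after J591 administration", while Section 10.1 (Visit 4) says "The date of scan (3 or 4 days vs 6-8 days after J591 infusion) will be assigned at the time of randomization". Section 9.2.1.1.1 and the study calendar give only the overall range of 2 to 8 days.

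**The concern.** How well a scan images metastases depends on two things: how many of the metastases it showed, and how many of the sites it showed were not metastases. The planned labels bear on the second question only in part and on the first not at all. A lesion that appears on bone scan, CT or MRI at a place where J591 was clean never enters the imaging result. A J591 site with a negative biopsy, or one that stays clean on every later scan, is not told apart from a site that has simply not been followed for long.

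The protocol's own account of earlier work (Section 2.1) uses a denominator of men with disease: targeting in all 30 phase I patients with radiographic disease, and in 31 of 32 men in the phase II trial. The present plan defines no such denominator, so a favourable list of confirmed sites could not be set against what was missed. With so few cases, rules written after the scans have been compared would carry little weight.

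**Working it through.** Section 13.4 gives no sample size, precision or accuracy figure for imaging, so there is nothing to reproduce. The check sets the labels against the outcomes that can occur.

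| J591 scan | Later evidence | Label in Section 13.4 |
|---|---|---|
| Uptake | Seen on conventional imaging | *positive* |
| Uptake | Biopsy shows metastasis | *definite* |
| Uptake | None yet, short follow-up | *possible* |
| Uptake | None after long follow-up | *possible* |
| Uptake | Biopsy negative | none of its own |
| No uptake | Metastasis on conventional imaging | none |
| No uptake | No metastasis | none |

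**What each measure needs**

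- Sensitivity = confirmed / (confirmed + missed). The missed count has no label.
- Negative predictive value = no uptake and no metastasis / all with no uptake. Neither count is planned.
- False-positive rate = uptake without metastasis / all without metastasis. Refuted uptake is not isolated, and the denominator is not planned.
- Confirmed fraction = (*positive* or *definite*) / all J591-positive. This is available, and is a lower bound on positive predictive value.

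**How many reference cases there could be.** Inputs from Section 13.1 are 34 and 17 men and 18-month metastasis-free survival of 80% and 50%. Events by month 18 = 34 × 0.20 + 17 × 0.50 = 6.8 + 8.5 = 15.3. This is a ceiling: Section 13.1 counts death as an event, and only selected sites scan.

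**Same output, different detection rates.** The documents give no detection rate. Assume 8 cases with a confirmed J591 finding:

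| Missed (assumed) | Sensitivity | Exact 95% CI |
|---|---|---|
| 0 | 8/8 = 100% | 63% to 100% |
| 2 | 8/10 = 80% | 44% to 97% |
| 4 | 8/12 = 67% | 35% to 90% |
| 7 | 8/15 = 53% | 27% to 79% |

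The *positive* and *definite* counts are identical in all four rows.

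**What *possible* hides.** Take the same 8 confirmed and assume 4 *possible*. The confirmed fraction is 8/12 = 67%. If all 4 were real, the predictive value would be 12/12 = 100%. The labels do not say how many of the 4 had been refuted.

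**Time between scan and reference.** The infusion is about 4 weeks into treatment and the scan follows within 2 to 8 days, so at roughly month 1. Lesions first seen at the 6-, 12- and 18-month imaging are then about 5, 11 and 17 months after the J591 scan (6 − 1, 12 − 1, 18 − 1).

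**Early scan window.** Section 9.2.1.1.2 gives days 2 and 3, and Section 10.1 gives days 3 and 4. They share only day 3. The late window, days 6 to 8, agrees. Day 5 lies in neither window, although it is inside the overall range.

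**The case against.** The strongest reply is that this is an exploratory question of yield and lead time at selected sites, not a diagnostic-accuracy study. Section 13.4 frames it as the possibility of finding sites that conventional imaging does not show, and leaves imaging out of its opening list of secondary endpoints. That reply stands in part. A reader might infer from the missing categories that the imaging objective cannot be estimated at all. The documents do not support this: the number of J591-positive sites, the share later confirmed and the interval to conventional detection all follow from the plan. A reader might also infer that unconfirmed uptake has no label, but *possible* is that label. Nor do men with metastases unseen on J591 vanish from the trial. They count in the primary endpoint and are absent only from the imaging labels.

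A second reply is that a reference standard at month 18 is not clean. A lesion first seen then may not have existed at the week-4 scan. In the 177Lu arm the imaged activity is also the treatment, so a true site may never show on CT or bone scan, and calling it an imaging error could count a treatment effect as a failure. Reporting by isotope exposes this problem but does not remove it. This objection is sound, and it limits how the added table may be described. It is not a reason to leave the counts out.

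A third reply is that Section 13.4 plans no comparison by scan window, that Section 9.2.1.1.2 says its days are approximate, and that both early windows lie within 2 to 8 days. This also stands, so the window conflict is secondary and does not by itself prevent estimation.

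**Conclusion.** The concern holds in a limited form. The labels classify only what J591 showed, so sensitivity, negative predictive value and a false-positive rate cannot be obtained from the planned output, and refuted uptake is mixed with uptake still awaiting evidence. Yield, confirmed fraction and lead time are unaffected.

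In the illustration, one set of label counts is compatible with detection rates from 53% to 100%. That range rests on an assumed 8 confirmed cases and 0 to 7 missed. The ceiling of about 15 events rests on the design rates, on every event being a metastasis and on every man being scanned, so the usable number will be smaller. The primary analysis is not touched.

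The two definitions of the early scan window are a genuine contradiction between Sections 9.2.1.1.2 and 10.1. Its weight is small as the analysis is now planned.

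**What to change.** In Section 13.4, keep the three labels and add:

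- **A category for metastases without J591 uptake**: those first seen on conventional imaging at a place with no uptake on the original central J591 read, each reported with the time since the J591 scan.
- **A split of *possible*** into biopsy-negative, no correlate through month 18, and insufficient follow-up.
- **A per-man two-by-two table among scanned men**: original J591 read (positive or negative) against radiographic metastasis by month 18, with exact confidence intervals, by isotope. Men without metastasis whose imaging stops before month 18 should be shown on a separate line.

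State beside the table that late lesions may postdate the scan and that in the 177Lu arm an uncorroborated site may reflect treatment effect. The table therefore describes association with later metastasis and is not pure diagnostic accuracy.

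The cost is SAP wording and a small extra analysis. The table uses the J591 reads and the primary-endpoint imaging already planned, and needs no unblinded re-read of J591 images. Matching lesion locations for the first category may need conventional imaging reports or images from sites, since Appendix E makes central review of those images optional. The intervals will be wide: 12 of 15, for example, has an exact 95% interval of 52% to 96%.

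Separately, reconcile Sections 9.2.1.1.2 and 10.1 on the early scan window. No window is proposed here.
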